Appendix 2. Definition of infections:

Acute nasopharengitis (Common cold); was defined when nasal stuffiness or drainage, sore or scratchy throat, sneezing, hoarseness, cough, with or without fever and headache were present which resolved in 7-10 days.

American Academy of Pediatrics Subcommittee on Management of Sinusitis and Committee on Quality Improvement. Clinical practice guideline: Management of sinusitis. Pediatrics 2001;108:798.

Acute otitis; was defined when acute onset of earache with erythema and limited mobility of the tympanic membrane determined by pneumatic otoscopy was present.

Tonsillitis; was defined when inflammation of one or both tonsils associated with a catarrhal exudate over the tonsil or the discharge of caseous or suppurative material from the tonsillar crypts was present

Viral croup; was defined when hoarseness, stridor and the characteristic "croupy" or barking cough developed after a viral prodrom by 12 to 72 hours of low-grade fever and coryza and resolved within one week.

Pneumonia; was defined when fever, cyanosis, and more than one of the following signs of respiratory distress: tachypnea, cough, nasal flaring, retractions, rales, and decreased breath sounds were present with abnormal chest X-ray. (5,12,13). Pneumonia was diagnosed when tachypnea occured in a patient younger than two years with a temperature higher than 38°C temperature. Children without fever or symptoms of respiratory distress didn't have the diagnosis of pneumonia.

Ostapchuk M, Roberts Dm, Haddy R. Community-Acquired Pneumonia in Infants and Children. Am Fam Physician 2004;70: 899-908.

Respiratory infections were also considered as mild or severe according to validated published criteria. Mild ARTIs involved the acute nasopharyngitis (common cold), tonsillitis or viral croup. Severe ARTIs involved the sinusitis, acute otitis or pneumoniae. Antibiotics were prescribed in the case of tonsillitis, otitis, sinusitis or lower ARTI.

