STUDY PROTOCOL

Effect of Vaxoral[®] (OM-85) on frequency of upper respiratory tract infections and size of adenoid tissue in preschool children with adenoid hypertrophy

Study Product(s)	Vaxoral [®] (OM-85)			
Indication	Recurrent RTIs, adenoid hypertrophy			
Sponsor	[name] Maternity and Children Research and Training			
	Hospital, Department of Pediatric Allergy and Immunology,			
	Ankara, TURKEY			
Anticipated	Taulasa			
Countries	Turkey			
Introduction	OM-85 significantly reduces RTIs in children. This effect was			
	proved by many clinical studies and meta-analyses ¹ . A Cochrane			
	meta-analysis first published in 2006 and updated recently (Del-			
	Rio-Navarro 2012) showed that immunostimulants (IS) could			
	reduce acute RTIs (ARTIs) by almost 39% when compared to			
	placebo. Among the different IS, OM-85 showed the most robust			
	evidence with 4 trials of "A quality" according to the Cochrane			
	grading criteria. Pooling six OM-85 studies, the Cochrane review			
	reported a mean number of ARTIs reduction by -1.20 [95% CI: -			
	1.75, -0.66] and a percentage difference in ARTIs by -35.9% [95%			
	CI: -49.46 , -22.35] compared to placebo ¹ .			
	Adenoid hypertrophy (AH) is one of the most important respiratory			
	disease in preschool children ² . In normal conditions adenoid tissue			
	enlarges up to 5 years and become smaller afterwards. But in some			
	children who have recurrent URTIs, it keeps growing and this can			
	be associated with complications ² . AH may cause recurrent			
	respiratory infections and each infection contributes to enlargement			
	of adenoid tissue thus promoting a vicious cycle. Additionally			
	enlarged adenoids are known to be reservoir for microbes and cause			
	of recurrent or long lasting RTIs ³ .			
	AH is associated with chronic cough, recurrent and chronic			

sinusitis, recurrent tonsillitis, recurrent otitis media with effusion, recurrent other respiratory problems such as, nasal obstruction and sleep disturbances, sleep apneas²⁻³. Eventually, AH causes loss of appetite and growth delay; it is often associated with misuse or over use of antibiotics and often eventually requires surgery. It decreases quality of life both in children and parents and it represents a burden not only for families but also for HCS and society due to increased health cost⁴.

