	• Reduction of number of RTIs within 12 months		
	Secondary Objective(s):		
	Reduction in duration of RTIs		
	Reduction of antibiotic use		
	• Reduction of absenteeism (missed school days or missed days of		
	work for parents)		
	Adenoid and tonsil health survey		

 Reduction of the size of adenoid tissue (described in appendix 3) Reduction of surgery need Design, incl. This is a randomised, double-blind, placebo-controlled, parallel group, phase IV study. First group will receive OM-85 (10-10-10 standard treatment regimen) Second group will receive matching placebo at the same posology (10-10-10). A second cure of treatment will be given 6 months after inclusion. Patients will be recruited from 01 September 2017 to 01 March 2018. The trial will begin in September 2017 and will be completed in March 2019. By this way every patient will be studied over all seasons (1 year study). Children (age: 2-6 years) Who experienced recurrent RTIs (at least 3 episodes in 6 months before the inclusion) Who have symptoms of AH (snoring; mouth breathing awake; mouth breathing asleep; nasal congestion; hyponasal voice; chronic nasal discharge; daytime drowsiness, or hyperactivity; restless sleep; sleep apnoca <15 sec; night cough; and poor oral intak/weight loss) based on the symptoms score questionnaire (described in appendix 1). Exclusion Criteria A Atopy Gastroesophageal reflux Immune deficiency Asthma or allergic rhinitis 		-					

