Appendix 1. Study Forms

Table 1. Demographic charecteristics

PATIENT FOLLOW-UP FORM		
Date		
Patient Number		
Treatment group (Randomisation code)		
Name Surname		
Birth date		
Gender		
Smoking at home		
Family history of asthma		
Family history of atopy		
DPT		
lgG		
IgA		
lgE		
IgM		
FIRST VISIT		
RTIs in previous 12 months		
RTIs in previous 6 months		
Number of hospitalisation in previous 12 months		
Total days of hospitalisation in previous 12 months		
Total days of absenteisim from school		
Total days of absenteisim from work for mother		
Total days of absenteisim from work for father		
Antibiotic use in previous 12 months		
Number of box		
Total number of days		
Symptome score		

QoLQ (Score)	
Adenoid size	
Radiological (AC/SP ratio)	
Nasopharingoscope (perceived percent obstruction of the choana)	

Table 2. Symptomes score (will be completed for each month)

Symptomes	none (0 point)	rarely (1 point)	frequently (2 points),	constantly (3 points)
Snoring				
mouth breathing awake				
mouth breathing asleep				
nasal congestion				
hyponasal voice				
chronic nasal discharge				
daytime drowsiness, or hyperactivitiy				
restless sleep				
sleep apnea <15 sec				
night cough				
poor oral intake/weight loss				

Scores from eleven symptoms were added together to provide a total symptom score of 33.

Table 3. Infection form (will be completed for each infection)

Type of RTI	
Duration of RTI	
Antibiotic consumption (days)	
Days of absenteism from school	
Days of absenteism from work for family members	

Table 4. Tonsil and Adenoid Health Status Survey (It will be completed by the parents in every
3 months)

TONSIL AND ADENOID SURVEY

We are conducting a study on children with tonsil or adenoid problems, and we are interested in the type of health problems that your child is having related to his (her) tonsils and adenoids. There are no correct or incorrect answers, and your opinion is most important to us. The survey is completely voluntary and will take about 3 minutes to complete.

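### Can long-standing adenoid symptoms be counted as common colds in the primary RTI count?

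*Protocol*

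**What the plan says.** The primary endpoint (Protocol, Endpoints) is the cumulative number of RTIs over 12 months. Appendix 2 says what counts. A common cold "was defined when nasal stuffiness or drainage, sore or scratchy throat, sneezing", hoarseness and cough, with fever and headache optional, and the symptoms "were present which resolved in 7-10 days". Croup has a time limit of the same kind ("resolved within one week") and also an onset element ("developed after a viral prodrom by 12 to 72 hours"). Otitis "was defined when acute onset of earache" with findings at the eardrum. Sinusitis needs upper respiratory infection symptoms, glossed as rhinoviral illness, that either fail to improve after 10 days or worsen after 5 to 7 days with purulent discharge.

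The Inclusion Criteria require AH symptoms from a list that includes "nasal congestion; hyponasal voice; chronic nasal discharge" and night cough. In Appendix 1, Table 2, parents score these monthly on a four-step frequency scale that runs up to constant.

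Under Procedures, families come to the clinic when RTI symptoms appear so that the type can be diagnosed. The notes under the visit schedule give this task to paediatric allergy and/or ENT specialists on the research team. Duration is recorded for each infection (Table 3) and by RTI type at the quarterly visits (Table 5).

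**The concern.** The children have symptoms at entry that resemble a cold, and the Introduction says "AH is associated with chronic cough, recurrent and chronic" sinusitis. The cold definition asks neither for acute onset nor for a change from the child's usual state, although the otitis and croup definitions have onset wording. It sets no minimum number of symptoms. At the diagnostic visit nobody can know whether the symptoms will resolve in 7-10 days, so the clause could be taken as a description of a typical cold. Little beyond the word acute in the name would then separate a new cold from the child's background symptoms.

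Two things would be at stake. AH attendances counted equally in both arms would add noise and cost power. If treatment also eased AH symptoms directly, the RTI count would fall with no infection prevented. That would blur the trial's hypothesis that fewer RTIs lead to smaller adenoids.

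**Working it through.** **1. The definitions against the AH symptom list**

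- *Overlap.* Stuffiness or drainage and cough match three of the 11 Table 2 items: nasal congestion, chronic nasal discharge and night cough. Sore throat, sneezing and hoarseness match none.
- *Time clause.* It is part of the defining sentence, as in the croup entry. Constant AH symptoms do not resolve in 7-10 days and so fail. Duration is recorded in Tables 3 and 5, so the clause can be checked once the episode is over.
- *Number of symptoms.* Only fever and headache are marked optional. Read strictly, the other symptoms are all required, and AH symptoms alone would not qualify. A looser reading, on which some of them suffice, lets a short flare of congestion, discharge or cough through.
- *Sinusitis.* Both routes start from an upper respiratory infection, and the second requires worsening. Unchanged background symptoms meet neither.

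Three questions remain unwritten: how to treat an AH flare that settles within 7-10 days; whether an episode that does not resolve is reclassified; and whether a cold that becomes sinusitis is one RTI or two.

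**2. The plan's own sample size**

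Inputs (SAP, Sample Size and Statistical method): difference 2.0 RTIs, SD 2.55, two-sided 0.05, 27 per group, 20% dropout.

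For a two-sample t-test, the noncentrality is 2.0 / (2.55 × √(2/27)) = 2.88 on 52 degrees of freedom, with critical value 2.007. Power is 0.807. At 26 per group it is 0.792, so 27 is the smallest size that reaches 80%. Then 27 / 0.8 = 33.75, which rounds up to 34 per group and 68 in total. The plan's figures reproduce.

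**3. What wrongly counted AH attendances would do**

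Let m be the mean number per child-year, equal in both arms and independent of true RTIs. The documents give no value for m, so the values below are assumptions. The difference stays at 2.0 and the SD becomes

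- Poisson: √(2.55² + m)
- rate varying between children with coefficient of variation 1: √(2.55² + m + m²)

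| m | SD (Poisson / varying) | Power, 27 per group | Power, 34 per group |
|---|---|---|---|
| 0 | 2.55 | 0.81 | 0.89 |
| 0.5 | 2.65 / 2.69 | 0.78 / 0.76 | 0.87 / 0.85 |
| 1 | 2.74 / 2.92 | 0.75 / 0.70 | 0.84 / 0.80 |
| 2 | 2.92 / 3.54 | 0.70 / 0.53 | 0.80 / 0.63 |

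The 27-per-group column assumes the full 20% dropout; the 34-per-group column assumes none. If the SD of 2.55 already contains such attendances, the losses are smaller.

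**4. If treatment also reduced these attendances**

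With an assumed reduction r of 25-50%, the added apparent benefit is m × r: 0.25 to 0.5 RTIs at m = 1, and 0.5 to 1.0 at m = 2. Against the planned 2.0 that is 12.5% to 50%. It requires AH to ease without any infection being prevented, whereas the Rationale expects smaller adenoids to follow from fewer infections.

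**The case for a change.** The best opposing case does not depend on how the time clause is read. Even as a criterion, it leaves room for AH symptoms that come and go, since Table 2 also has rare and frequent as answers. An episode that outlasts 10 days may be relabelled sinusitis and still count. Taken literally, a cold over in 5 days would not be an RTI, so the primary count would depend on duration, a secondary endpoint. Table 3 has no onset or end date with which to settle disputes later, and a written rule would cost only a few sentences.

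Some of this stands. A short flare could be called a cold, and no written rule tells the assessor how to decide. The literal 5-day problem is weaker: beside the croup wording, the clause reads sensibly as an upper limit, so a shorter cold still counts. The move to sinusitis is limited by the requirement that the symptoms be those of an infection.

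The obvious rewrite is not a clear gain. Declaring the durations to be mere description and counting only symptoms clearly worse than usual would replace a limit that can be checked against recorded duration with a judgement made against a monthly frequency scale. It would still set no minimum number of symptoms.

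**Conclusion.** The concern does not hold in its main form. As written, constant AH symptoms do not meet the cold definition, and unchanged background symptoms do not meet the sinusitis definition. The three open counting questions are ordinary missing detail. Specialists see the child at each reported episode, the trial is double-blind and there is one centre, so whatever convention they follow should apply alike to both arms.

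The possible cost cannot be derived from the documents. Power between 0.78 and 0.53 at 27 per group, and an inflation of 12.5% to 50% of the planned difference, rest on assumed attendance rates, an assumed spread between children and an assumed treatment effect on AH symptoms. The lowest power needs two false episodes per child-year, wide variation between children and the full 20% dropout together. The sample size is not in error. The conclusion rests on reading the 7-10 day clause as part of the definition, which is where the text puts it, and on clinic diagnosis being carried out as Procedures describes.

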	gamma globulins, or anticonvulsive drugs within the				
	previous 6 months.				
Endpoints	Primary Endpoint: Cumulative number of RTIs over the 12				
	months.				
	monuis.				
	Secondary Endpoints:				
	• Duration in days of RTIs				
	• Antibiotic use (n. of cycles and days)				
	Missed school/work days				
	• Adenoid and tonsil survey (described in appendix 1 of the				
	original protocol)				
	• Size of adenoid tissue over the 12 months according to				
	radiographic and flexible nasopharyngoscopic evaluation (described				
	in appendix 3 of original protocol).				
	Surgery need				
	• AEs				
	Patients will be recruited from 01 September 2017 to 01 March				
Procedures	2018. The trial will begin in 01 September 2017 and will be				
	completed 01 March 2019.				
	Children with the ages of 2-6 years who have recurrent RTIs and				
	AH will be evaluated for the eligibility for the study. When eligible				
	for the study, children's all demographic characteristics will be				
	recorded (Table 1). Eligible children will be evaluated by ear-nose-				
	throat (ENT) specialist and flexible laryngoscopy and radiographic				
	evaluation of adenoid size will be performed in order to measure the				
	adenoid size. All children will be evaluated by an allergy specialist.				
	Complete blood count, serum IgG, IgA, IgE, IgM will be measured.				

Skin prick test will be performed with common allergens.

All children will be randomized into two study arms (active treatment and placebo). OM-85 3.5 mg capsule or placebo will be given according to the standard treatment schedule (10-10-10) for the three consecutive months. All patients will receive 2 cures of treatment at the beginning and 6 Months after inclusion in the study. Every patients will be followed-up for 12 months.

Patients (and care giver/parents) will be given a symptom score form (Table 2) in order to record all nasal symptoms, signs and duration of RTIs, antibiotic use, days of absenteeism from school and from work for family members, monthly.

All patients will be asked to come to the clinic when they have symptoms of RTI in order to diagnose the type of RTIs. Then they will be asked to complete the infection form during the acute RTIs (Table 3).

Every 3 months they will fill in the Tonsil and Adenoid Health Status Survey (Table 4).

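### Appendix 2 builds length of illness into the case definitions of the common cold and croup, so a treatment effect on duration can change the primary RTI count

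*Protocol*

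**What the plan says.** The Endpoints section of the protocol gives "Primary Endpoint: Cumulative number of RTIs over the 12" months. A secondary objective is "Reduction in duration of RTIs", with the matching endpoint "Duration in days of RTIs".

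The infection types are set out in Protocol Appendix 2. Three of its entries use time:

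- Acute nasopharyngitis: a list of symptoms that "were present which resolved in 7-10 days".
- Viral croup: hoarseness, stridor and a barking cough after a prodrome of "low-grade fever and coryza and resolved within one week".
- Sinusitis: persistent URTI symptoms "without improvement after 10 days or a worsening of symptoms after 5 to 7 days", together with further signs. This is a condition on persistence, not on when the illness ends.

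Otitis, tonsillitis and pneumonia carry no condition on length.

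Under Procedures, families come to the clinic when the child has "symptoms of RTI in order to diagnose the type of RTIs". Table 3 is completed for each infection and records its type and duration. Table 5 collects number and duration every 3 months under six codes (AOM, AS, AT, AN, AC, P), with no column for any other RTI. The SAP contains no rule for counting episodes.

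**The concern.** When the length of an episode decides whether it meets a definition, an outcome of the trial selects the episodes that enter another outcome. The selection happens after treatment starts, so randomisation and blinding do not remove it.

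Treatment could then move episodes across a boundary without preventing or causing any. Colds shortened to under 7 days would leave the count. Slowly improving colds shortened from more than 10 days to 10 or fewer would enter it, as would croup shortened to a week or less. The cold part of the duration endpoint would be taken from episodes already confined to 7-10 days. At stake are the reading of the primary result and of one secondary result.

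**Working it through.** **1. Do the definitions leave gaps?** Take Appendix 2 literally.

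| Episode | Cold | Croup | Sinusitis | Place on Table 5 |
|---|---|---|---|---|
| Plain cold, clears day 5 | No, under 7 days | No | No | None |
| Cold, improves slowly, clears day 12 | No, over 10 days | No | No, it was improving | None |
| Croup, clears day 8 | No | No, over one week | No | None |

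**2. The plan's own figure.** The sample size uses a difference of 2.0 RTIs, SD 2.55, two-sided 0.05 and 80% power. The normal approximation gives 2 × (1.960 + 0.842)² × 2.55² / 2.0² = 25.5, so 26 per group. The noncentral t gives 79.2% power at 26 and 80.7% at 27. Then 27 / 0.8 = 33.75, so 34 per group and 68 in total. The stated figures reproduce.

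**3. Size under the literal window.** The documents give no cold lengths, share of RTIs that are colds, or 12-month placebo rate. Assumptions: both arms have the same true number of colds; lengths are whole days of at least 1, from a normal distribution with mean m and SD s; a cold counts only at 7 to 10 days; treatment shortens every cold and does nothing else. The counted share is

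S(m, s) = [Φ((10.5 − m)/s) − Φ((6.5 − m)/s)] / [1 − Φ((0.5 − m)/s)].

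Example with s = 2: S(8) = (0.894 − 0.227)/1.000 = 0.668 and S(7) = (0.960 − 0.401)/0.999 = 0.559. The ratio is 0.84, a 16% fall.

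| Mean length, placebo → treated | SD 2 | SD 2.5 | SD 3 |
|---|---|---|---|
| 8 → 7 days | −16% | −12% | −8% |
| 9 → 8 days | 0% | 0% | 0% |
| 10 → 9 days | +20% | +14% | +10% |
| 8 → 6 days | −42% | −31% | −23% |

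The sign changes because the window is centred on 8.5 days: moving towards that centre adds counted colds, and moving away removes them.

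**4. In RTIs per child per year.** Assume 6 to 8 RTIs (the entry criterion of at least 3 in 6 months gives 6 if it continues) and 50 to 80% colds. That is 6 × 0.5 = 3.0 to 8 × 0.8 = 6.4 colds. For 8 → 7 days the counted share falls by 0.04 (SD 3) to 0.11 (SD 2). The false difference is 3.0 × 0.04 = 0.12 to 6.4 × 0.11 = 0.70 RTIs, against the planned 2.0. For 10 → 9 days a change of about the same size goes the other way.

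**5. A different assumption for long colds.** Suppose every cold over 10 days is still counted, as sinusitis, so that only the 7-day floor acts. With gamma lengths, means 7 to 9 and SD 2 to 3, a 1-day shortening then always lowers the count. The false difference is 3.0 × (0.443 − 0.322) = 0.36 to 6.4 × (0.669 − 0.467) = about 1.3 RTIs.

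**6. Duration.** In the model of step 3, mean length per counted cold falls from 8.36 to 8.10 days (SD 2) or from 8.43 to 8.30 (SD 3) when the true change is 8 → 7. A true 1-day effect shows as 0.26 or 0.13 day. If the endpoint is instead total cold days per child, the change is 0.837 × 8.10/8.36 − 1 = −19% (SD 2) or 0.917 × 8.30/8.43 − 1 = −10% (SD 3), against a true −1/8 = −12.5%. For 10 → 9 days the total would rise by 0.102 to 0.195 in count terms, net +9 to +16% after the shorter mean length (8.70 to 8.57 and 8.90 to 8.64 days), against a true −10%.

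**The case against.** A reader might infer that colds under 7 days are excluded from the primary endpoint, and that the trial therefore cannot tell fewer infections from shorter ones. The documents do not support either statement.

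- **No exclusion is written.** The Endpoints section counts RTIs without reference to Appendix 2, and no step removes an episode afterwards.
- **The procedure points towards counting.** The type is diagnosed while the child has symptoms, before the length is known. Table 3 is completed for each infection. The 7-10 days may only describe the usual course of a cold and mark it off from sinusitis.
- **The contrast with croup proves little.** Croup reads "coryza and resolved within one week", an upper limit only, which might suggest that the cold entry means a lower limit as well. Appendix 2 is loosely drafted from several sources, and this difference in wording does not establish intent.
- **The effects can be separated if short colds are entered.** Type and duration are recorded per infection, so counts with and without the time limits could be compared.
- **The duration endpoint is not necessarily flattened.** That holds for mean length per counted cold. It does not hold for total days, and Table 5 could be read as collecting a total.

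All of this stands, and it limits the point to an ambiguity with consequences. It does not remove it. Appendix 2 is headed as a set of definitions, nothing says that short colds count, and staff who diagnose at the visit must either ignore the time limit or re-classify later. The protocol does not say which. Short colds that are never entered cannot be recovered.

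**Conclusion.** The point holds in a conditional form. If Appendix 2 is applied as written, length of illness decides whether some colds and long croups count, so an effect on duration can leak into the primary count. Otitis, tonsillitis and pneumonia are unaffected.

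Neither size nor direction can be fixed from the documents. For a 1-day shortening with no effect on incidence, counted colds change by −8 to −16%, about 0, or +10 to +20% for placebo means of 8, 9 and 10 days. These percentages apply to colds, not to all RTIs. Under the added assumptions on rate and cold share, the 8-day case is about 0.1 to 0.7 RTI per child per year. It is 0.36 to 1.3 across means of 7 to 9 days if all long colds are kept as sinusitis. Both are below the planned 2.0, but not negligible beside it. It should be settled in the text because the remedy costs little, not because a bias has been shown.

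**What to change.** In Protocol Appendix 2:

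1. Remove resolution time as a condition for counting.
2. Count each episode that meets the symptom criteria for acute nasopharyngitis or croup at the clinic visit as one RTI, whatever its length.
3. Re-type an episode as sinusitis only if the Appendix 2 sinusitis criteria are met.
4. Keep the 7-10 days and the one-week limit as description of the usual course, and say so.
5. Take the duration endpoint from the actual days on Table 3.

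The SAP can repeat the counting rule in one sentence.

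The cost is a change of wording in two definitions, with no extra visits or forms. The planned difference and SD are not tied to a cold length, so the sample-size arithmetic stays as it is. The downside is that short, mild colds count, so the mean RTI count may be somewhat higher than under the strict definition. If description was all that was intended, the change only records it.
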